7.2.4. Missing and Partial Data

Participants who drop out will not be replaced. All reported data will be included in the summaries without imputation of any missing data. Any missing data for diary data for cataplexy attacks and Nausea Visual Analog Scale (NVAS), or any missing item score for Epworth Sleepiness Scale (ESS) will be treated as follows:

- For participants experiencing at least 1 day of non-missing cataplexy attack, the weekly number of cataplexy attacks will be derived as the average number of daily attacks from days with non-missing data within the week, multiplied by 7. Note: 1 or more daily entries in the cataplexy attack dairy are required to be completed for the weekly average cataplexy attack calculation. Otherwise, the weekly score is recorded as missing.
- For participants with at least 1 day of NVAS data, the NVAS for that week will be the average daily score from days with non-missing data within the week, then multiplied by 7.
- For participants experiencing 3 or more ESS item scores missing at a specific timepoint, the ESS total score will be set to missing. If 1 or 2 ESS item scores are missing at a specific timepoint, the mean of remaining 7 or 6 non-missing ESS item scores at that timepoint will be used to impute the missing ESS item value. ESS total score will be calculated as the sum of the observed and imputed item scores.

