9.4.2. Effectiveness Endpoints

Effectiveness endpoints will be summarized descriptively. The following effectiveness endpoints will be assessed in this study:

- Change in weekly rate of cataplexy attacks: Participants will be required to complete an electronic Cataplexy Frequency Diary ([Appendix 5](#)) daily. Based on these data, the weekly rate of cataplexy attacks (for NT1) will be established. Additionally the change in weekly cataplexy rate from the last week of the Baseline period (on Xyrem) to that of individual weeks during the Open Label Conversion and Treatment Optimization Period will be summarized. For participants experiencing at least 1 day of cataplexy attack, the weekly number of cataplexy attacks will be derived as the average number of daily attacks from days with non-missing data within the week, multiplied by 7.
- Change in Epworth Sleepiness Scale (to assess EDS): Changes in ESS scores between the Baseline period and ET or E/D, as applicable, will be summarized.
- Participant Global Impression of Change: PGIC values will be measured at the ET or E/D, as applicable, in accordance with the SoA ([Section 1.3](#)). The number of participants with each response will be summarized. Additional categorization of the scores may be performed and summarized.
- Time to optimized dose and regimen is defined as the time from the first dose and regimen to the optimized dose and regimen of XYWAV, where the optimized dose and regimen indicates the final dose and regimen that remains unchanged throughout the remainder of the Intervention (Open-label Conversion and Treatment Optimization) period. Compliance is not considered in the derivation of the time to achieve optimized dose and regimen. The time to achieve optimized dose and regimen will be summarized.
- Additionally, the number of changes from the first dose and regimen to optimized dose and regimen, the number of participants dosing fasted versus dosing without consideration of food, and the timing and characterization of meals with regard to dosing of XYWAV ([Appendix 4](#)) will be summarized descriptively.

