The NVAS ([Appendix 6](#)) evaluation was developed for this study, and will be performed daily over the last 7 days of the Xyrem-stable Baseline period and the last 7 days on XYWAV of the Intervention period prior to ET visit or prior to the E/D, if possible. For participants with at least one day of NVAS data, the NVAS for that week will be the average daily score from days with non-missing data within the week, then multiplied by 7. The mean of each assessed 7-day period will be summarized and the change from the mean of the Baseline period to the mean of the Intervention period will be summarized.

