7.6. Changes to Planned Analyses

The changes in planned analyses between the protocol and SAP are the following:

- All Screened Analysis Set, XYWAV Safety Analysis Set and XYWAV Efficacy Analysis set are added in addition to the analysis sets defined in protocol section 9.3. Exclude potential screen failures from Enrolled Analysis Set defined in protocol section 9.3.
- National Cancer Institute (NCI) common terminology criteria for adverse events (CTCAE) version 5.0 or higher is added as the reference for AE severity classification.

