10.8. Nausea Visual Analog Scale

Tolerability associated with Xyrem and XYWAV will be measured based on an NVAS assessment.

For NVAS, the baseline value is defined as NVAS evaluation performed daily over the last 7 days of the Xyrem-stable Baseline Period. For missing NVAS assessment handling, please see Section 7.2.4. The NVAS results for the baseline, end of treatment, and the change from the baseline period will be summarized with number and frequency of having nausea or not, and the mean (SD), median, and range. 95% CI of the mean change in NVAS from the baseline will be estimated. A listing will also be presented.

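### Under the SAP's only NVAS derivation, nausea results would be reported at 7 times the daily line participants marked, with no label saying so

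*SAP*

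**What the plan says.** Section 7.2.4 of the SAP derives the weekly NVAS for every participant with at least one day of data: "the NVAS for that week will be the average daily score from days with non-missing data within the week, then multiplied by 7". The SAP contains no other NVAS derivation.

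SAP 10.8, the endpoint section, states: "For NVAS, the baseline value is defined as NVAS evaluation performed daily over the last 7 days of the Xyrem-stable Baseline Period". It names no mean, sum or factor. Its pointer to the rule reads: "For missing NVAS assessment handling, please see Section 7.2.4". It then asks for the number with and without nausea, the mean (SD), median and range at baseline and end of treatment, and the change. It adds: "95% CI of the mean change in NVAS from the baseline will be estimated".

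Protocol 9.4.4 carries the same times-7 rule and follows it with a statement of what is reported: "The mean of each assessed 7-day period will be summarized". The change score is described in the same terms, as a difference between the means of the two periods.

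SAP 7.6 opens with "The changes in planned analyses between the protocol and SAP are the following" and has no NVAS entry.

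The factor has the same form as the cataplexy rule in protocol 9.4.2: "the average number of daily attacks from days with non-missing data within the week, multiplied by 7". In SAP 4.2.1 the cataplexy endpoint is named as a weekly rate, while the nausea endpoint is named only as a change in the scale. Protocol Appendix 6 asks the participant to mark one point on a line for nausea over the past 24 hours.

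**The concern.** A participant marks a daily line, and the table will show numbers on a scale 7 times as long under the name NVAS. Multiplying by 7 suits cataplexy, where a weekly count is the stated quantity. For a severity line it gives a pro-rated 7-day total, which neither document calls by that name or gives a range for.

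This matters because no hypothesis is tested, so the reported size is the result. Protocol 2.1 lists better nausea tolerability among the questions on which evidence will be collected. Protocol 9.4.4 says the NVAS was developed for this study, and the documents give no reference values for it. A reader can judge a change only against the line itself. Someone who takes the protocol's sentence about means at face value would expect the daily scale and would misread a times-7 result as a much larger level or change. Interim results may be presented externally (protocol 9.5, SAP 5.5), so an interim and a final report could also differ by 7 if the wording were resolved differently each time.

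**Working it through.** The documents give no NVAS figure to reproduce. The check is arithmetic on the two candidate period values, followed by a reading of the text.

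**Inputs.** From the documents: a 7-day window in each period (protocol 8.3.6 and 9.4.4), use of non-missing days only, and at least one scored day required (SAP 7.2.4). Assumed: the daily scores, SD, sample size and line length. The line in Appendix 6 is not visible in the text available, so I use 0-100 and 0-10.

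**Formulas.** Let m be the mean of a participant's non-missing daily scores.
- Daily-scale value: B = m
- SAP 7.2.4 value: A = 7 × m
- A / B = 7 for any scores and any number of scored days, provided m is not 0

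**Complete weeks (assumed, 0-100 line).**
- Xyrem: 20, 25, 15, 20, 20, 10, 30. Sum 140, m = 20, A = 140.
- XYWAV: 15, 20, 10, 15, 15, 10, 20. Sum 105, m = 15, A = 105.
- Change: 15 − 20 = −5 on the daily scale; 105 − 140 = −35 under the SAP rule.
- The same pattern on a 0-10 line (2.0 and 1.5) gives −0.5 and −3.5.

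**Weeks with gaps (assumed).**
- Xyrem: 10, 20, missing, 10, 20, 10, 20. m = 90/6 = 15, A = 105.
- XYWAV: 5, 10, 5, missing, missing, 10, 10. m = 40/5 = 8, A = 56.
- Change: −7 or −49. The ratio is again 7, so gaps do not alter it.

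**Range.** On a 0-100 line A runs from 0 to 700; on a 0-10 line, from 0 to 70. In the first example the baseline value of 140 is already past the end of the line.

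**Group level (assumed mean change −5, SD 15, n = 90; normal-approximation CI, the type named in SAP 7.4).**
- Daily scale: SE = 15/√90 = 1.581; CI = −5 ± 1.96 × 1.581 = −8.10 to −1.90.
- Times 7: mean −35, SE 11.068, CI −56.69 to −13.31.
- Estimate/SE = −3.16 on both scales.

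With an assumed mean change of −2, SD 15 and n = 100, the CI is −4.94 to 0.94 on the daily scale and −34.58 to 6.58 times 7. Both include 0. Whether the interval excludes 0 is thus the same on either scale.

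**Nausea yes or no.** Since 0 × 7 = 0, and a positive score stays positive, this count does not change.

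**Reading the text.** Within the SAP the result is effectively fixed. The 7.2.4 rule covers complete weeks as well as weeks with gaps, 10.8 refers to it, and no unmultiplied NVAS value is defined. In the protocol, the sentence after the rule speaks of the mean of a 7-day period and the change between two such means. Its natural sense is a participant's mean over 7 days, because what gets summarized is normally a set of participant values.

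**The case against.** The best defence is that protocol 9.4.4 is consistent. Its first sentence derives a participant's weekly value, and its second reports the group mean of that value. On this reading the times-7 value is not left derived but unused, and the SAP dropped nothing, so SAP 7.6 had nothing to record. This reading is possible. A reader might infer that the protocol plainly defines two rival NVAS values; the documents make that likely, but do not establish it.

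It can also be said that the SAP is not ambiguous in practice. That largely stands: times 7 is what a programmer following 7.2.4 would produce. Because the rule sits under missing data, and 10.8 cites it only for that purpose, a reader might infer that the factor applies only to incomplete weeks. A constant daily score of 10 would then give 10 for a complete week and 70 for a week with one day missing. The wording of 7.2.4 does not support this, since it covers anyone with at least one scored day.

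Finally, the effect is a change of unit. No NVAS threshold, responder rule or test depends on it, and the multiplied value is a valid pro-rated total. That stands too, and it limits the severity. It does not answer the missing label: a total reported only as NVAS will be read against the line.

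**Conclusion.** The point holds as a minor one. Under the SAP as written, the NVAS mean, SD, median, range, change and CI limits would be exactly 7 times the daily line and could exceed its maximum, with nothing to identify them as a 7-day total. They would also differ by 7 from the most natural reading of the protocol's summary sentence.

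The factor of 7 needs no assumption about the data. Only the illustrations rest on assumed scores and line lengths: a mean daily change of 1 to 10 units would be reported as 7 to 70. A reader might infer a calculation error, bias or lost precision. The documents do not support that, because direction, estimate/SE, whether the CI excludes 0, and the nausea count are the same on both scales. Only the reported magnitude and its interpretation are at stake.

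**What to change.** - **SAP 7.2.4:** remove the multiplication by 7 for NVAS and keep it for cataplexy.
- **SAP 10.8:** define each period value as the mean of the non-missing daily scores over the last 7 days of Baseline and over the last 7 days on XYWAV. Compute the change and its 95% CI from these.
- **SAP 7.6:** record the change.
- **Protocol 9.4.4:** align the wording at the next amendment.

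The cost is a few lines of SAP text and a logged departure from the protocol's times-7 wording. Data collection does not change. The protocol edit can wait, since amendments need IRB/IEC approval.

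If a 7-day total is what the sponsor wants, keep the factor. In that case, label the value in SAP 10.8 as a pro-rated 7-day sum, give its range (7 times the daily range), and reconcile it with the sentence about means in protocol 9.4.4.

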7.3. Hypotheses Testing

All endpoints (listed in Section 4.2) will be summarized descriptively. Formal hypothesis testing will not be performed.

7.4. Level of Significance & Multiplicity Adjustment

As this study does not test a formal hypothesis, there is no multiplicity adjustment. For specific statistics, for example, difference in proportions, 95% CI based on normal approximation will be generated.

7.5. Subgroups and Subgroup Analyses

Subgroup analyses will be performed when applicable. See Section 9.1.7.

7.6. Changes to Planned Analyses

The changes in planned analyses between the protocol and SAP are the following:

- All Screened Analysis Set, XYWAV Safety Analysis Set and XYWAV Efficacy Analysis set are added in addition to the analysis sets defined in protocol section 9.3. Exclude potential screen failures from Enrolled Analysis Set defined in protocol section 9.3.
- National Cancer Institute (NCI) common terminology criteria for adverse events (CTCAE) version 5.0 or higher is added as the reference for AE severity classification.

8. STUDY POPULATION SUMMARIES

8.1. Enrollment

The total number and percentage of participants for each Analysis Set defined in Section 6 will be summarized. The number of participants who enrolled by country and study site/Investigator will be summarized.

8.2. Subject Disposition

All participants who provide informed consent will be accounted for in this study. For each period, the number and percentages of participants who entered, received at least one dose, completed, are still ongoing (for interim analyses), and early discontinuation, including reasons for discontinuation, will be presented using the enrolled analysis set.

Note that coronavirus disease 2019 (COVID-19) impacts throughout the study will be captured at each non-remote visit for the type of visit performed due to COVID-19 and study related impacts due to COVID-19. These will be summarized by visit based on enrolled analysis set.

8.3. Demographic and Baseline Characteristics

Demographic and other baseline characteristics data will be summarized using descriptive statistics for the safety analysis set.

Demographic and other baseline characteristics include:

- The age entered by the sites will be used. If it is missing, then it will be derived from date of birth and informed consent date. (For countries where regulations allow only the year of birth to be entered for birth date, July 1st of that year will be used for the calculation of age).
- Gender
- Race participants who reported more than one race will be reported under 'multiple' race category

- Ethnicity
- Childbearing potential
- Baseline weekly cataplexy attack rate
- Baseline ESS score

8.4. Medical/Surgical History

Surgical and medical history will be coded using the Medical Dictionary for Regulatory Activities (MedDRA) dictionary, version 24.0, and are defined as those medical conditions/ diseases which started prior to or on the date of initial ICF signing.

Medical/surgical history data will be summarized by system organ class (SOC) and preferred term (PT) for the safety analysis set. If a participant reports a past medical condition/disease, surgery or past medication more than once within a SOC or PT, the medical condition/disease, surgery or past medication will be reported only once for that SOC or PT.

8.5. Prior and Concomitant Medications

Medications will be coded to the preferred drug name using the World Health Organization (WHO) drug dictionary, version GLOBALB3Mar21, and will be classified as follows:

- Prior medications are defined as any medications which started prior to the first dose of XYWAV.
- Concomitant medications will be defined as any medications with a stop date on or after the first conversion from Xyrem to XYWAV, during the study, or any medication that is ongoing. A medication with completely missing use dates or partially missing use dates without evidence that the medication was stopped prior to the first dose of study drug will be considered a concomitant medication.

Prior and Concomitant medications will be summarized by preferred drug name based on the safety analysis set. A listing will also be presented.

8.6. Protocol Deviations

Protocol deviations as classified in the CTMS (type of deviation and severity) will be summarized across all study periods using enrolled analysis set.

Changes to study conduct due to COVID-19 restrictions will be reported as protocol deviations and summarized. All protocol deviations will also be provided in a listing.

These COVID-19 related deviations will be summarized separately by the classification type in CTMS and included in a listing.

9. EFFECTIVENESS

9.1. Key Effectiveness Endpoints and Analysis

Unless otherwise specified, effectiveness data will be primary summarized using both the XYWAV Safety Analysis Set and XYWAV Efficacy Analysis Set.

9.1.1. Rate of Cataplexy Attacks

Narcolepsy Type 1 (NT1) participants will be required to complete an electronic Cataplexy Frequency Diary daily. The weekly rate of cataplexy attacks is derived as the average number of daily attacks from days with non-missing data within the week multiplied by 7. The baseline value for cataplexy attack is the weekly rate of the last week of the baseline period on Xyrem. For example, if the first dose of XYWAV is taken in the night of Day 16, the last week of baseline would be approximately Day 10 to Day 16, prior to the time of first dose of XYWAV. After conversion, the weekly rate for each visit will be based on the days within the visit window as in Section 7.2.3.

Weekly rate for baseline and each visit will be summarized with number of participants, mean, SD, median, min and max. Changes in weekly cataplexy rate from the study baseline to that of each visit during the intervention period will be summarized with number of participants, mean, standard deviation, median, minimum, and maximum. Changes in weekly cataplexy rate from the XYWAV baseline to that of each visit after XYWAV conversion during the intervention period will be also summarized in a similar manner. Box-whisker plot weekly rate of cataplexy attack will be plotted over time.

Cataplexy attack rate will only be determined for NT1. If NT2 participants provide cataplexy attack diary data, those data will be listed but excluded from the summary of the endpoint.

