This current study (JZP258-401) is a multi-center, open-label, single-arm, phase 4 trial that seeks to build upon the demonstrated benefits of XYWAV and provide further descriptive evidence of safety, effectiveness, tolerability and treatment optimization in participants switching from Xyrem to XYWAV. The study will include comparative assessments related to treatment-based and exposure-related adverse events (AE), tolerability, and therapeutic effectiveness of disease control between Xyrem and XYWAV. Participants will be switched from Xyrem to XYWAV at the same dose and regimen as Xyrem. Once the investigator determines that a stable dose and regimen of XYWAV is achieved, participants will be allowed to dose with or without food. If needed, XYWAV will be titrated to an optimized dose and regimen based on efficacy and tolerability, under the advisement and instruction from the investigator.

Success in this study will be indicated by seamless switching of the majority of participants from Xyrem to XYWAV, with little or no changes in dose strength or regimen. Additionally, evidence will be provided to support participant preference for XYWAV based on its lower level of sodium, potentially improved tolerability profile, a safety profile typical of oxybate, and similar disease control as participant's current Xyrem dose and regimen. Collectively, these data are expected to expand the knowledgebase of clinical experience in the population of participants with narcolepsy transitioning from Xyrem to XYWAV.

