7.1. Discontinuation of Study Intervention

If study intervention is permanently discontinued, the participant will not remain in the study, other than for safety follow-up. See the SoA for data to be collected at the time of discontinuation of study intervention and safety follow-up, and for any further evaluations that need to be completed.

A participant must be discontinued from study intervention for any of the following reasons:

- The participant or participant's legal representative requests to discontinue study intervention
- The participant develops an AE or other safety or clinical concern that may compromise the participant's continued participation
- The participant's alcohol screen result is positive
- The participant's urine drug screen test result is positive for any prohibited drugs in this study (see [Section 5.2](#), Exclusion Criterion, 17)
- The participant has a positive serum pregnancy test ([Appendix 3](#) and [Section 8.3.5](#))
- The participant is non-compliant with study intervention or procedures
- The sponsor terminates the study prior to completion
- The investigator determines the participant should not continue on study intervention
- The participant enrolls in a different clinical study that involves investigational treatment considered by the sponsor to be incompatible with Study JZP258-401

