7.2.3. Visit Windows

Except where specified, all data will be summarized using the CRF visit at which the data was collected. Where data is captured at an Early Termination visit, those data will be summarized with the regular visit at which the assessment would have been captured, relative to the study period during which the participant withdrew. For example:

- If a participant early discontinues during the Baseline Period, i.e. prior to the first dose of XYWAV, then data should be mapped to Visit 3.
- If a participant early discontinues during the Intervention Period, i.e. after at least one dose of XYWAV, then data should be mapped to the next scheduled visit at which those data would have been captured, based on the Schedule of Assessments.

For data captured independent of a CRF visit, eg, Adverse Events, Concomitant Medications and Cataplexy Diary, the following rules will apply:

- If the reported date is on or prior to first dose of XYWAV then the data will be considered to be included into the Xyrem Baseline Period for summaries
- If the reported date is after the first dose of XYWAV while on or prior to the completion of treatment or early discontinuation, then the data will be considered to be included into the XYWAV Intervention Period for summaries.

Unscheduled visits in general will not be mapped (excluded from analyses) when the corresponding scheduled visit is present. Unscheduled visits will only be mapped when the scheduled visit is missing. If more than 1 unscheduled assessments are available, choose the one with the assessment date closer to the target study day specified below, if 2 assessments are equally close to the target day (but on different sides), the latter assessment will be chosen. In addition, unscheduled visits with the assessment date earlier than the date of first dose of XYWAV, or participants early discontinue the study prior to the first dose of XYWAV, the data can only be mapped up to Visit 3. If the assessment date is later than the date of first dose of XYWAV, the unscheduled data should not be mapped to any visit prior to Visit 3.

Study Period	Study Visit	Target Study Day
Baseline	Visit 2	1
Intervention	Visit 3	15

Intervention	Visit 4	22
Intervention	Visit 5	29
Intervention	Visit 6	36
Intervention	Visit 7	43
Intervention	Visit 8	57

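### Cataplexy has no end-of-XYWAV value, so its Visit 8 figure omits participants who stop by about Day 43, whereas the end-of-treatment ESS and NVAS results can include them

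*SAP*

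**What the plan says.** **Cataplexy.** SAP 9.1.1 states "Changes in weekly cataplexy rate from the study baseline to that of each visit during the intervention period will be summarized", and adds that after the switch "the weekly rate for each visit will be based on the days within the visit window as in Section 7.2.3". Protocol 9.4.2 has the same structure: the change runs from the last Xyrem week to "that of individual weeks during the Open Label Conversion and Treatment Optimization Period will be summarized". Neither lists a value at end of treatment (ET) or early discontinuation (E/D).

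**Missing data.** SAP 7.2.4 says "All reported data will be included in the summaries without imputation of any missing data". It then makes an exception within a diary week: if at least one day was completed, the mean of the completed days is multiplied by 7. A week with no entry stays missing. SAP 9.1.6 plans no sensitivity analysis.

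**Who is counted.** SAP 9.1 reports effectiveness in two sets: XYWAV Safety (at least one XYWAV dose) and XYWAV Efficacy (those of them who finish the study). Under Protocol 7.1, "If study intervention is permanently discontinued, the participant will not remain in the study, other than for safety follow-up".

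**ESS.** Protocol 9.4.2 says "Changes in ESS scores between the Baseline period and ET or E/D, as applicable, will be summarized". For someone who stops during the Intervention period, SAP 7.2.3 says "data should be mapped to the next scheduled visit at which those data would have been captured". After the switch ESS is next scheduled at ET, which is Visit 8.

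**NVAS.** Protocol 9.4.4 takes the last seven days on XYWAV before ET or, if possible, before E/D. SAP 10.8 reports this as one end-of-treatment value.

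**The concern.** The objective is to describe how people fare when they switch, and Protocol section 2 expects "similar disease control as participant's current Xyrem dose and regimen". A reader of the report will naturally set the last cataplexy value beside the end-of-treatment ESS and NVAS values, all under the same analysis-set label. The plan lets early stoppers into the last two but gives them no route into the first unless they stop late.

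Two things follow. First, if NT1 participants leave because their cataplexy has worsened (Protocol 2.3.1 lists worse disease control as a risk of switching), their results are missing from the last cataplexy figure, and it moves towards maintained control. Second, presenting both the all-dosed and the completer set would normally expose such an effect. At Visit 8 the two sets contain almost the same people, so their agreement could be mistaken for robustness. The data may be used in label discussions (Protocol 4.1), and interim data may be presented externally (Protocol 9.5).

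**Working it through.** The plan states no figure on this point, so there is none to reproduce. The check traces the mapping rules and then gives an illustration.

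**1. Who can reach the Visit 8 value.** Inputs from SAP 7.2.3: target days 15, 22, 29, 36, 43 and 57 for Visits 3 to 8. With the first XYWAV dose on the night of Day 15, possible early stop days are 16 to 56, that is 56 − 16 + 1 = 41 days. SAP 7.2.3 gives target days but no window bounds, so two readings are shown for the diary.

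| Measure and reading | Stop days that reach Visit 8 | Share of 41 |
|---|---|---|
| ESS, E/D value sent to the next visit where ESS is due | 16–56 (41) | 100% |
| Cataplexy, E/D mapping applied to the diary | 44–56 (13) | 32% |
| Cataplexy, diary days assigned by date, final week taken as Days 51–57 | 51–56 (6) | 15% |

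Under the mapping reading the other 28 stop days go to Visits 4 to 7, seven to each. Under either reading, nobody who stops on or before Day 43 is in the Visit 8 cataplexy value. Actual visit dates can shift that day slightly.

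**2. What the two analysis sets can show.** Assumptions: 70 NT1 participants dosed, 10% (7) stop early, stop days spread evenly. Completers number 70 − 7 = 63. Visit 8 in the XYWAV Safety set then has:

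- by date: 63 + 7 × 6/41 = 64.0
- by mapping: 63 + 7 × 13/41 = 65.2

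A last-week-on-XYWAV value could include up to 70. The two sets therefore differ at Visit 8 by one or two people, not seven. This ignores anyone who reaches Visit 8 but misses the follow-up visit.

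**3. Illustrative size.** Let *d* be the share stopping, *g* the amount by which stoppers' last on-XYWAV change is worse than that of completers, and *f* = 28/41 the share of stoppers absent from Visit 8 under the mapping reading. Set the completers' mean change to 0.

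- All-dosed last-week mean = *d* × *g*
- Visit 8 mean, all stoppers absent = 0, so the difference is *d* × *g*
- Visit 8 mean, mapping reading = *d*(1 − *f*)*g* / [(1 − *d*) + *d*(1 − *f*)]

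For *d* = 0.10 and *g* = 5, the all-dosed mean is 0.50. The mapped Visit 8 mean is 0.0317 × 5 / 0.9317 = 0.17, and the difference is 0.33.

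| Share stopping (*g* = 5 attacks/week) | All stoppers absent | Mapping reading |
|---|---|---|
| 5% | 0.25 | 0.17 |
| 10% | 0.50 | 0.33 |
| 20% | 1.00 | 0.63 |

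In the 10% case, comparing the two sets at Visit 8 would show a gap of 0.17 at most, against an all-dosed value 0.50 above the completers.

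**4. Whether the needed rule exists.** SAP 7.2.3 already defines a last week on XYWAV for an early stopper: with a first dose on Day 15 and a stop on Day 20 it is Days 16–20, which is 20 − 16 + 1 = 5 days. It refers the short week to SAP 7.2.4. Section 9.1.1 does not use this rule to form a cataplexy summary.

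**The case against.** The plan never names Visit 8 as the final or main cataplexy result. The endpoint is a time course, the study is descriptive, and no test or numerical criterion depends on that visit. Early stoppers contribute at the visits before they stop, n is shown at each visit, and box plots are drawn over time. In that sense cataplexy shows more of a stopper's course than ESS or NVAS. Discontinuations are tabulated with reasons (SAP 8.2), and SAP 9.1.7 splits cataplexy by whether an optimized dose was achieved, which places many early stoppers in a group of their own. All of this stands and limits the weight of the point. The optimized-dose split does not restore the missing values, however: that group's Visit 8 cataplexy figure lacks its early stoppers too.

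The contrast with ESS and NVAS is also less than complete. SAP 9.1.2 names only the ET visit, so including E/D values rests on SAP 7.2.3 together with Protocol 9.4.2 and needs an attended E/D visit. NVAS before E/D is collected only if possible, so an abrupt stopper may have none.

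A reader might infer that the Visit 8 figure covers only those still on study at the end. The documents do not support that: someone who stops after Visit 7 may contribute, through the E/D mapping or through diary days near Visit 8.

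A reader might also infer a known bias in XYWAV's favour. That is not supported either. Several stopping reasons in Protocol 7.1, such as a positive alcohol or drug screen, pregnancy or non-compliance, need not relate to cataplexy.

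**Conclusion.** The structural point holds and needs no assumed number. Cataplexy has no end-of-XYWAV summary; its Visit 8 value in the all-dosed set leaves out NT1 participants who stop by about Day 43; and comparing the two analysis sets at that visit cannot reveal the effect of dropout. ESS and NVAS are built so that early stoppers can enter their end-of-treatment results.

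Size and direction are unknown. The range of 0.17 to 1.0 attacks/week assumes 5% to 20% stopping, a gap of 5 attacks/week and, at its lower end, evenly spread stop days and the same gap for early and late stoppers. If stopping is unrelated to cataplexy, the expected shift is zero. Because the analysis is descriptive and the loss is visible in n, this is a modest improvement and not a flaw that undermines the study.

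**What to change.** In SAP 9.1.1 add one summary row, *Last week on XYWAV (ET or E/D)*, derived with the last-week rule already in SAP 7.2.3, for all NT1 participants in the XYWAV Safety Analysis Set who have post-switch diary data. Show:

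- the weekly rate and its change from baseline
- the number of diary days contributing (or time on XYWAV)
- the number of dosed NT1 participants with no post-switch diary data

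State that this row is the one to read beside the end-of-treatment ESS and NVAS results, and keep the by-visit table as the time course.

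The cost is SAP wording and one table row from diary data already collected up to ET or E/D (Protocol 8.2.1). The downside is that the row mixes different durations on XYWAV, and very early stoppers contribute only a few conversion-phase days scaled to a week. That is why the day count belongs beside it.
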